9.3.3 Analysis related to primary objective

9.3.3.1 Primary endpoint

The primary endpoint is the change in patient-assessed pain intensity from baseline to 24-72 hours (average of the assessments performed at 24, 48 and 72 hours) for the patients' first flare.

The comparison of primary interest is between anakinra (100 mg and 200 mg combined) and triamcinolone, and the null and alternative hypotheses with regard to this are defined as:

$H_0: \mu_{\text{anakinra}} = \mu_{\text{triamcinolone}}$

$H_A: \mu_{\text{anakinra}} \neq \mu_{\text{triamcinolone}}$

The primary endpoint will be estimated using a mixed model repeated measures analysis with the measurements on the individual time points as responses (baseline, 6, 12, 18, 24, 48 and 72 hours), and with treatment (anakinra 100 mg, anakinra 200 mg and triamcinolone), ULT use (yes/no), BMI (<30.0 and ≥ 30.0 kg/m²), visit and treatment-visit-interaction as fixed effects and center as random effect. An unstructured covariance matrix will be used to account for within-subject correlation. The estimated mean change from baseline to 24-72 hours for each treatment group (anakinra and triamcinolone), the estimated difference between the groups and the associated 95 % confidence interval and p-value based on this model will be presented.

The assumptions of normality and homogeneity of variance will be assessed by inspection of normal probability plots and residual plots.

The primary efficacy analysis mixed model repeated measures approach assumes that the underlying missing data mechanism is missing at random (MAR). Since the MAR assumption may not hold, a tipping point analysis will be used for performing sensitivity analysis under the missing not at random (MNAR) assumption. For data that is missing, a shift parameter (with a range of values) will be added to imputed values. This will assess the value of the shift parameters, for anakinra and triamcinolone, which would overturn the conclusions of the primary analysis. The tipping point analysis will assume that the missing outcomes on anakinra and triamcinolone will vary independently including scenarios where the dropouts on anakinra have worse outcomes than triamcinolone.

The full details of the sensitivity analyses to assess the robustness of the primary analysis will be pre-specified in the SAP.

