## **5 Changes from protocol affecting the statistical analysis**

According to the protocol, AEs and SAEs will be classified as occurring during ADA presence when the starting date for the AE is within the time period after the latest negative assessment until next negative assessment with a positive assessment of ADA in between. Instead AEs and SAEs will be presented by ADA positive and ADA negative patients for the whole study period.

The relationship between ADA and efficacy and the relationship between ADA and IL-Ra/anakinra concentrations over time will also be explored which was not described in the protocol.

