### 14.1.2.2 Sensitivity to missing data handling

The primary efficacy analysis MMRM approach assumes that the underlying missing data mechanism is MAR. When the assumption of missing data being MAR is valid, the treatment effect estimated from the MMRM analysis is unbiased. However, this assumption may not hold in all circumstances and the possibility that the missingness mechanism is missing not at random (MNAR) should be explored (EMA 2010, National Research Council 2010, Little et al 2002, O’Kelly et al 2014). A sensitivity analysis will be performed to assess the robustness of results from the primary analysis to potential deviations from the MAR assumptions.

In this sensitivity analysis a distinction is made between intermittent missing values and monotone missing values. Intermittent missing values for a variable Y means that some values may be missing, say  $Y_j$  is missing, while there are values observed for the same patient at a later time point, i.e.  $Y_k$  is observed for some time point  $k > j$ . Patients with intermittent missing values are said to have a non-monotone missing data pattern. Monotone missing values are missing values where  $Y_j$  being missing implies that all  $Y_k$ ,  $k > j$ , are missing for that patient. A patient with only monotone missing values (and no intermittent missing values) is said to have a monotone missing data pattern.

In the sensitivity analysis, intermittent missing data are assumed to be MAR, while monotone missing values are assumed to be MNAR in the anakinra treatment groups. The analysis assumes that the missing outcomes on the different treatment arms vary independently, and includes scenarios where monotone missing values in the anakinra treatment arms have worse outcomes than monotone missing values in the triamcinolone treatment arm. Missing data in the triamcinolone group will be assumed to be MAR (intermittent as well as monotone missing values).

The tipping point analysis involves multiple imputation methodology, where each of the imputed datasets is analysed based on the same statistical model used for the primary analysis, i.e. a MMRM analysis of pain intensity VAS at time points baseline, 6, 12, 18, 24, 48 and 72 hours based on the ITT population.

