### 14.1.2.3 Tipping point analysis

The sensitivity analysis will be based on a tipping point approach to assess how severe the departures from the MAR assumption must be in order to overturn a statistical significant result

to a non significant result for the primary analysis. This is done by evaluating several assumptions for the missing data mechanism until the tipping point is reached, i.e. where the study's conclusion changes. The deviation from the MAR assumption is reflected in the shift parameter. If the shift parameter at the tipping point is plausible the conclusions of the primary analysis under the MAR assumption is questionable.

For monotone missing data, the initial shift value will be zero, which represents MAR. The shift will remain at zero for the triamcinolone treatment group. For the anakinra treatment groups, the shift will be increased, and the process repeated until the study's conclusion changes, i.e. treatment effect is no longer significant.

The following steps show the process for the tipping point analysis:

1. Missing VAS values will be imputed based on the Markov-Chain Monte Carlo (MCMC) method (assuming MAR).

In this step, 500 complete datasets will be generated.

2. For subjects with monotone missing data in the anakinra treatment arms, monotone missing values will be imputed based on a MNAR model by adding a delta value to the MAR imputed value. Delta adjustment will be based on a scaled delta-adjustment approach in which the delta value added at each time point is defined as a percentage of the mean pain VAS at that time point. For the the triamcinolone group monotone missing values, imputed based on the MAR assumption in the first step, will not be adjusted.

In this step, the 500 datasets with complete data generated in step 1 will be updated.

3. The MMRM model used in the primary analysis will be fitted to the 500 imputed datasets generated in step 2. As in the primary efficacy analysis, the VAS scores from time points baseline, 6, 12, 18, 24, 48 and 72 hours will be included as response. Specification of the model and the contrast of primary interest will match the primary efficacy analysis. From each analysis of an imputation dataset, adjusted estimates of means, mean treatment differences and p-values will be obtained.

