4. The results from the MMRM analyses of the 500 imputed datasets will be combined to obtain an overall estimate of the contrast of primary interest, i.e. the mean difference between the anakinra groups and the triamcinolone group in change from baseline to 24-72 hours in pain VAS score, as well as the p-value obtained after accounting for the uncertainty introduced by the missing data.
5. Steps 2 to 4 will be repeated by gradually increasing the values for the scaled delta adjustment until the scaled delta value is found that gives a p-value exceeding 0.05 (2-sided) or greater.

In the first step of the delta-adjustment, missing values are imputed based on a MCMC method assuming MAR. The MCMC sampling will be performed as implemented in PROC MI in SAS. The MCMC method will include a single chain with a burn-in of 1000, a thinning of 100 and non-informative priors for all parameters.

Treatment group and strata (ULT usage and BMI) are included in the variable list in the MCMC step. In this implementation, numeric dummy variables are created and included in the variable list together with the VAS pain intensity variables for time points 0, 6, 12, 18, 24, 48 and 72 hours. Because these dummy variables are observed for all patients, they are not imputed in the MCMC step, but contribute to the imputation model to allow for the mean pain intensity at different time points to depend on treatment and strata, while assuming the covariance structure across treatment and strata. This corresponds to the assumptions made in the analysis model used for the primary analysis.

In the second step, monotone missing values in the anakinra treatment arms are delta-adjusted where a delta value is added to the MAR imputed value. This approach corresponds to the third approach for pattern imputation with delta adjustment described [in Ratitch et al. \(2013\)](#).

The delta is defined in terms of percentage of the mean value at a given time point. Because the mean VAS pain intensity changes with time, the delta added to the MAR-imputed missing values will be different for different time points. Imputed values will be truncated at 100, since this is the maximum value possible for a VAS pain intensity measure. No rounding of values is performed in the imputation step.

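### The SAP's tipping-point analysis drops the triamcinolone shift that the protocol plans, without declaring it, and does not exempt baseline from the delta

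*SAP*

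**What the plan says.** Protocol 9.3.3.1 describes a tipping-point analysis in which a shift over a range of values is added to imputed data: "This will assess the value of the shift parameters, for anakinra and triamcinolone, which would overturn the conclusions of the primary analysis". It adds that "missing outcomes on anakinra and triamcinolone will vary independently including scenarios where the dropouts on anakinra have worse outcomes than triamcinolone", and leaves the full details of the sensitivity analyses to the SAP.

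SAP 14.1.2.2 repeats the principle: "The analysis assumes that the missing outcomes on the different treatment arms vary independently". The same paragraph then treats every missing triamcinolone value, intermittent or monotone, as MAR. SAP 14.1.2.3 carries this through: "The shift will remain at zero for the triamcinolone treatment group". Only monotone missing values on anakinra are shifted, by a delta set at each time point as a percentage of the mean VAS there. Time 0 is among the imputed variables. Delta rises in 5% steps, "gradually increasing the values for the scaled delta adjustment until the scaled delta value is found that gives a p-value exceeding 0.05". On the cap: "Imputed values will be truncated at 100, since this is the maximum value possible for a VAS pain intensity measure". The analysis is run only for comparisons that are significant to begin with.

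SAP Section 5, the list of changes from the protocol, covers anti-drug antibodies only. One entry reads "Instead AEs and SAEs will be presented by ADA positive and ADA negative patients for the whole study period"; the other adds antibody explorations. The tipping point is not mentioned.

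**The concern.** This is the only MNAR analysis of the primary endpoint. A reader of the protocol expects an answer in two dimensions: how much worse anakinra dropouts, and how much better or worse triamcinolone dropouts, would have to be to overturn the result. The SAP gives one line of that grid. Removing a named shift parameter is a change of method, and Section 5 is where a reader would look for it. If triamcinolone loses more patients than anakinra, the direction left out could be the more fragile one.

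The delta rule raises a second, smaller question. The endpoint is follow-up minus baseline. If a missing baseline is raised by the same percentage as the follow-up values, and baseline pain is higher, the intended penalty becomes a benefit.

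**Working it through.** **Inputs from the documents.** SAP Section 7: 106 anakinra, 53 triamcinolone, difference 12 mm, SD 25 mm, two-sided 5%. Protocol 7.2.2.2: baseline VAS of about 70 mm in earlier gout studies. SAP 4.2: at most 169 randomized, including up to 10 extra patients for collection failures.

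**Assumptions (not in the documents).** Observed difference 12 mm; 24–72 h means of 40 mm on anakinra and 52 mm on triamcinolone; dropouts miss all three primary values. Ranges run from none to all of the lost information being recovered from earlier time points.

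**1. Planning figure.** A noncentral t calculation with 53 and 106 patients gives 80.9% power, so the stated 80% reproduces. SE = 25 × √(1/106 + 1/53) = 4.206 mm. With t(157 df) = 1.975 the critical difference is 8.31 mm, so a 12 mm result can lose 12 − 8.31 = 3.69 mm before it stops being significant.

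**2. Tipping rule.** Let mA and mT be the shares missing, δA the worsening of anakinra dropouts and δT the improvement of triamcinolone dropouts, both relative to MAR. The result tips when

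mA·δA + mT·δT = 12 − 1.975 × SE.

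The SAP sets δT = 0. If no information is recovered, SE = 25 × √(1/[106(1 − mA)] + 1/[53(1 − mT)]).

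**3. Equal dropout, anakinra-only run.** The last column adds the cap at 100 and the variance created by the shift.

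| Missing per arm | Loss needed (mm) | δA = loss/m (mm) | On the SAP's 5% grid |
|---|---|---|---|
| 10% | 3.24–3.69 | 32.4–36.9 | 85–95% |
| 15% | 2.98–3.69 | 19.8–24.6 | 50–65% |
| 20% | 2.69–3.69 | 13.5–18.5 | 35–50% |

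With equal m, only the sum δA + δT matters. Opposite shifts split the same gap about in half, so the second arm adds little.

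**4. Unequal dropout, anakinra 10% and triamcinolone 20%.** With no recovery, SE = √(625/95.4 + 625/42.4) = 4.614 and the loss needed is 12 − 9.11 = 2.89 mm. Anakinra-only: 2.89/0.10 to 3.69/0.10 = 28.9–36.9 mm. Triamcinolone-only: 2.89/0.20 to 3.69/0.20 = 14.4–18.5 mm. With truncation to 0–100 and the shift variance these become 29–37.5 and 15–19 mm.

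**5. Low anakinra dropout.** At 5% on anakinra, the cap leaves at most 100 − 40 = 60 mm per patient, or 0.05 × 60 = 3.0 mm on the arm mean. With 5% per arm the loss needed is 12 − 1.975 × 4.206/√0.95 = 3.48 mm with no recovery, up to 3.69 mm. In the fuller calculation no anakinra-only delta up to 400% tips. Opposite shifts of 35.5–38 mm do. With 10% missing on triamcinolone instead, triamcinolone-only shifts of 34.5–38.5 mm do.

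**6. Baseline.** A patient with no value from 0 to 72 h is monotone missing from time 0. For baseline 70 and follow-up 40 mm, a 25% delta adds 10 mm at follow-up and 17.5 mm at baseline, a net −7.5 mm. At a failure rate of 10/169 this is −0.44 mm on the anakinra mean before the cap. With the cap (baseline SD 13 mm and follow-up SD 25 mm assumed), follow-up means of 30/40/50 mm give 0.53/0.39/0.26 mm toward anakinra for 10 failures and 0.11/0.08/0.05 mm for 2. The sign reverses at deltas of about 103/79/66%. With baseline exempt, the same 25% delta and 10 failures give 0.44/0.58/0.71 mm against anakinra.

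**The case against.** The protocol delegates full details to the SAP, the SAP states its one-arm rule openly, and it is to be signed before the first database lock. The scenario the protocol names, worse anakinra dropouts, is the one that is run, and it is conservative for an anakinra win. All of that stands. A reader might infer that the SAP conceals the change or picks the easier test; the documents support neither. What remains is that a parameter the protocol names has gone, Section 5 is silent, and the independence sentence no longer describes the method. That sentence could mean only that anakinra shifts are not tied to triamcinolone, but in a paragraph that fixes triamcinolone at MAR it misleads.

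The shifts needed are often large. In the 5%/5% case anakinra dropouts would have to average about 74–75 mm and triamcinolone dropouts about 18–20 mm. Many would read that as robustness. The 10%/20% case needs a moderate shift, but supposes that one triamcinolone patient in five misses all three assessments despite reminder calls and a 72-hour visit. This objection stands as a limit on importance.

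On baseline, it is tempting to include every missing baseline foreseen in SAP 8.2. That reading fails: under SAP 14.1.2.2 a missing baseline with a later observed value is intermittent and stays MAR. Only the collection failures of Protocol 7.3.6 and SAP 4.2 are shifted, and 10 is the ceiling on extra randomizations, not a forecast.

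A reader might also infer that the search breaks down because it has no end. The cap makes results level off, and the SAP's own wording allows that a tipping point may not be found. What is missing is a stopping and reporting rule.

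**Conclusion.** The mismatch between protocol and SAP is established from the text, and it should be corrected. How much it matters cannot be established, because the documents give no missing-data rate. Under the assumptions above, the omitted direction adds little at equal dropout of 10–20%. It is about twice as fragile as the tested one at 10%/20% (15–19 against 29–37.5 mm). At about 5% anakinra dropout it is the only route to a tipping point, but one needing shifts of about 35–39 mm.

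The baseline rule has the wrong sign for a stress test at small and moderate deltas. Its effect, 0.05–0.53 mm at a 25% delta for 2–10 failures, is small beside the 2.7–3.7 mm needed to tip. The missing maximum delta is a matter of clarification. None of this touches the primary analysis.

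**What to change.** - On the same 500 imputations, run a two-way grid of independent anakinra and triamcinolone deltas, including triamcinolone dropouts better than MAR. Truncate to 0–100. Keep the present anakinra-only run as one line of the grid.
- State that baseline values are never delta-adjusted.
- If the one-arm version is kept, declare and justify it in SAP Section 5, delete the independence sentence from SAP 14.1.2.2, and still exempt baseline.
- As clarifications, state a maximum delta and report *no tipping point within range* where that applies. Also cover a significant result favouring triamcinolone: raising anakinra pain scores then only widens the difference, so the search as written cannot tip it.

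The cost is SAP text, some extra computing and a larger table. The stated robustness may look less favourable.

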## **14.2 Secondary endpoints supporting the primary objective**

The secondary endpoints supporting the primary objective will be analyzed using both the ITT population and the PP population.

### **14.2.1 Patient-assessed pain intensity in the index joint on a Visual analogue scale (VAS)**

To further evaluate the effect of anakinra, the change from baseline in pain intensity on VAS at 6, 12, 18, 24, 36, 48, 72 hours and at Days 5, 6, 7 and 8 for the first flare will be evaluated.

Pain intensity on VAS will be evaluated using a mixed model repeated measures analysis similar to the primary analysis with the measurements on the individual time points as responses (baseline, 6, 12, 18, 24, 36, 48 and 72 hours and Days 5, 6, 7 and 8), and with treatment (anakinra 100 mg, anakinra 200 mg and triamcinolone), ULT use (yes/no), BMI (<30.0 and  $\geq 30.0$  kg/m^2), visit and treatment-visit-interaction as fixed effects and center as random effect. For each time point, the estimated mean change from baseline for each treatment group (anakinra and triamcinolone), the estimated difference between the groups and the associated 95 % confidence interval and p-value based on this model will be presented.

The same order of covariance matrices as for the primary endpoint will be used, until convergence is met.

Graphs will be used to visualize the mean pain intensity on VAS estimated from the repeated measures model at each time point for each dose group of anakinra and triamcinolone and also by subgroups of BMI and ULT usage.

The observed patient-assessed pain intensity and change from baseline (VAS) in index joint at each time point will also be presented by descriptive statistics.

In addition, the percent change in observed pain intensity at 24, 48 and 72 hours will be visualized by graphically presenting the distribution of percent improvement. For each category of percent improvement (x-axis), the percentage of patients who improved (y-axis) will be plotted. Increments of 10 % will be used for the improvement ( $\geq 10$  %,  $\geq 20$  %,  $\geq 30$  %, etc).

#### **14.2.2 Patient-assessed pain intensity in the index joint on a 5-point Likert scale**

To further evaluate the effect of anakinra, the change from baseline in pain intensity on the Likert scale at 6, 12, 18, 24, 36, 48, 72 hours and at Days 5, 6, 7 and 8 for the first flare will be evaluated (see Section 18.18).

Pain intensity on the Likert scale will be evaluated using a mixed model repeated measures analysis similar to the primary analysis with the measurements on the individual time points as responses (baseline, 6, 12, 18, 24, 36, 48 and 72 hours and Days 5, 6, 7 and 8), and with treatment (anakinra 100 mg, anakinra 200 mg and triamcinolone), ULT use (yes/no), BMI (<30.0 and  $\geq 30.0$  kg/m^2), visit and treatment-visit-interaction as fixed effects. For each time point, the estimated mean change from baseline for each treatment group (anakinra and triamcinolone), the estimated difference between the groups and the associated 95 % confidence interval and p-value based on this model will be presented.

The same order of covariance matrices as for the primary endpoint will be used, until convergence is met.

Graphs will be used to visualize the mean pain intensity on the Likert scale estimated from the repeated measures model at each time point for each dose group of anakinra and triamcinolone.

The observed patient-assessed pain intensity and change from baseline (Likert) as well as observed patient-assessed pain intensity categories (Likert) in index joint at each time point will also be presented by descriptive statistics.

### 14.3 Secondary efficacy endpoints

The secondary efficacy endpoints for the 1st flare will be analyzed using both the ITT population and the PP population.

#### 14.3.1.1 Pain intensity for anakinra dose groups, 100 and 200 mg

The primary endpoint, change in patient-assessed pain intensity as measured by VAS from baseline to 24 to 72 hour for the first flare, will be evaluated for the 2 different anakinra doses (100 mg and 200 mg) in comparison to triamcinolone.

The effect of the 2 different anakinra doses will be evaluated using the same mixed model repeated measures model analysis as for the primary endpoint. The estimated mean change from baseline to 24 to 72 hours for each of the 2 anakinra doses (100 mg and 200 mg) and triamcinolone, the estimated differences anakinra 100 mg – triamcinolone and anakinra 200 mg – triamcinolone and the associated 95 % confidence intervals and p-values from the model will be presented.

The estimated mean change from baseline for the secondary endpoints (VAS and Likert pain intensity at each timepoint) supporting the primary endpoint for each of the 2 anakinra doses (100 mg and 200 mg) and triamcinolone, the estimated differences anakinra 100 mg – triamcinolone and anakinra 200 mg – triamcinolone and the associated 95 % confidence intervals and p-values from the model will also be presented.

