5.2 Study rationale

The main aim of this study is to evaluate the efficacy and safety of anakinra in patients for whom NSAIDs and colchicine are either contraindicated or not appropriate, not tolerated or do not provide an adequate response, and to select the appropriate dose in order to reduce the pain and inflammation of a gouty arthritis flare. The study will also evaluate the safety and immunogenicity of anakinra when treating subsequent flares during a 1-2 years study extension.

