6.2 Secondary objectives

To evaluate the primary endpoint and the secondary endpoints supporting primary objective for the 2 different anakinra dose groups compared to triamcinolone in the treatment of the first gouty arthritis flare.

To evaluate the time to onset of effect, time to response, time to pain resolution, time to rescue medication, physician's assessment of global response and clinical signs, patient's assessment of global response, inflammatory biomarkers and safety of anakinra compared to triamcinolone in the treatment of the first gouty arthritis flare both for the combined anakinra group (100 and 200 mg) and the 2 different anakinra dose groups.

To evaluate the primary and secondary endpoints and safety of the combined anakinra group (100 and 200 mg), the 2 different anakinra dose groups and triamcinolone in the treatment of subsequent flares. Subsequent flares are flares occurring after the first flare in the study and within 52 weeks of randomization of the last randomized patient in the study. However the extension will be a maximum of two years (104 weeks) after randomization for the individual patient in the study.

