7.2.4.2 Dose levels

In published case series of anakinra (see Section 10.2.1), different dose levels have been used. The majority of patients have been treated with once-daily s.c. injections of 100 mg anakinra with generally positive outcome. In the case series where patients were treated with 100 mg for 3 days, patient-assessed improvement of pain varied between 50 and 100 % (19).

In the 2 anakinra dose-response studies in patients with RA (30, 75, 150 mg (44) and 0.04, 0.1, 0.4, 1, 2 mg/kg (46)), the change from baseline in patient-reported pain intensity (a component of the primary efficacy endpoint) tended to increase with increasing doses, and the largest differences versus placebo were achieved at daily s.c. doses of 150 mg and 2 mg/kg, respectively.

Based on the results of the RA studies and the case series in acute gouty arthritis, 100 mg was selected as the lowest daily dose to be tested in this study.

The gouty arthritis population proposed to be indicated for treatment with anakinra is assumed to have a higher mean body weight than the RA patients. For reference, the mean (SD) body weight was 98 (18) kg in the canakinumab clinical studies in patients with acute gouty arthritis (N=368) (6), as compared to 77 (19) kg in the anakinra clinical study safety pool in RA patients (N=3330). As the anakinra clearance increases with increasing body weight, once-daily s.c. doses of both 100 and 200 mg will be evaluated in this study.

The safety profile of anakinra is well established and has been similar across indications and dose levels during long-term treatment (see section 5.1.4.2). Thus, a once-daily s.c. administration of 200 mg anakinra is not expected to result in an increased incidence of adverse events compared with 100 mg, the only exception being ISRs that, in studies of RA, were more frequent with s.c. doses above 100 mg.

The dose range chosen for this study may not allow discrimination based on statistically significant differences. The study will allow descriptive comparisons of efficacy and safety at 2 relevant dose levels.

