#### **14.1.1 Subgroup analyses**

In order to examine the consistency of the treatment effect, the MMRM model used for the primary analysis will also be used within the following subgroups, using the ITT population:

- ULT usage (yes/no).
- BMI ( $<30.0$  and  $\geq 30.0$  kg/m^2).
- Age ( $<65$  years and  $\geq 65$  years).
- Sex (male, female).
- Race (White and Other).
- Renal function (eGFR category  $\geq 90$ ,  $\geq 60 - <90$ ,  $\geq 30 - <60$ ).
- Usage of rescue medication up to 72 hours during for the first flare (yes/no).

For each subgroup, the estimated change in pain intensity in each treatment group (anakinra and triamcinolone), the estimated difference in change in pain intensity between treatments and the corresponding 95 % confidence intervals will be obtained from the model. P-values will not be presented. Further, the change in pain intensity will also be evaluated for the 2 anakinra doses for each subgroup.

The estimated difference in change in pain intensity between anakinra and triamcinolone and the corresponding 95 % confidence intervals will also be presented graphically in a forest plot.

To avoid too small subgroups in the analysis regarding race, American Indian or Alaska Native, Asian, Black or African American, Native Hawaiian or Other Pacific Islander will be grouped together with Other.

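### Dose selection is part of the study's main aim, but no 200 mg minus 100 mg difference with a confidence interval is planned; every between-group dose estimate is against triamcinolone

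*SAP*

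**What the plan says.** Protocol 5.2 gives as part of the main aim "to select the appropriate dose in order to reduce the pain and inflammation of a gouty arthritis flare". Protocol 7.2.4.2 warns that the chosen dose range may not separate the doses by statistical significance, and then states: "The study will allow descriptive comparisons of efficacy and safety at 2 relevant dose levels".

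The formal secondary objective in Protocol 6.2 is narrower. It asks for the primary and supporting endpoints "for the 2 different anakinra dose groups compared to triamcinolone in the treatment of the first gouty arthritis flare".

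The analyses follow the formal objective:

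- **Primary endpoint.** SAP 14.1 pools the two doses against triamcinolone, from a mixed model with a three-level treatment factor. SAP 14.3.1.1 adds "the estimated differences anakinra 100 mg – triamcinolone and anakinra 200 mg – triamcinolone", with 95% confidence intervals and p-values.
- **Other first-flare endpoints.** In SAP 14.3.1.2 to 14.3.1.9, the dose-specific hazard ratios, odds ratio and mean differences are likewise against triamcinolone.
- **Subgroups.** SAP 14.1.1 says "the change in pain intensity will also be evaluated for the 2 anakinra doses for each subgroup" but names no contrast between doses.
- **Results for each dose alone.** SAP 14.3.1.1 gives model mean changes "for each of the 2 anakinra doses (100 mg and 200 mg) and triamcinolone". SAP 14.1 plots each dose's mean change with its 95% interval. SAP 14.2.1 and 14.2.2 plot model curves by dose, and SAP 14.3.1.10 summarises subsequent flares by dose.
- **Multiplicity.** SAP 9.3 makes no adjustment.

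**The concern.** Choosing between 100 mg and 200 mg turns on the difference between them and how well it is known. The plan attaches a difference, an interval and a p-value to each dose against triamcinolone, and none of these to one dose against the other. The outputs that carry inference therefore answer whether each dose beats the comparator, not whether the doses differ.

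The risk is the familiar one of setting two p-values side by side. One dose can be significant against triamcinolone and the other not while the doses are practically the same. A report with those two p-values and no direct contrast leaves that misreading open.

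**Working it through.** **Inputs.** Protocol 9.1 and SAP 7: 53 patients per arm, SD 25 mm, design difference 12 mm, two-sided 5%, 80% power.

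**1. The plan's own figure.** For a 2:1 comparison, the triamcinolone group needs (1.960 + 0.842)² × 25² × (1 + 1/2) / 12² = 51.1, rounded up to 52, with 104 on anakinra. The plan has 53 and 106, which gives 81.4% power by the normal approximation (80.9% with the noncentral t). The sample size reproduces.

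**2. Precision of the missing contrast.**

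- SE(200 mg − 100 mg) = 25 × √(2/53) = 4.86 mm.
- 95% half-width = 1.96 × 4.86 = 9.5 mm, or 9.6 mm with a t quantile.
- If the SD were 20 to 30 mm (an assumed range), the normal half-width would be 7.6 to 11.4 mm.

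Because all arms have 53 patients, this nominal precision is the same as for each planned dose-versus-triamcinolone comparison. The pooled primary comparison has 1.96 × 25 × √(1/53 + 1/106) = 8.2 mm.

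**3. What a formal dose test could do.** At SD 25 mm, power is about 18% for a true dose difference of 5 mm and 54% for 10 mm. The difference detectable with 80% power is 2.80 × 4.86 = 13.6 mm. This agrees with the caution in Protocol 7.2.4.2 and is why an estimate, not a test, is the right request.

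**4. How often the planned p-values would disagree when the doses are identical.** Let both doses be better than triamcinolone by the same amount d. Each comparison has z-mean d/4.86. The two share the triamcinolone arm, so their correlation is (25²/53) / (2 × 25²/53) = 0.5. Then P(exactly one significant) = 2 × [P(one given dose significant) − P(both significant)], from the bivariate normal:

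| True d for both doses | P(given dose significant) | P(both) | P(exactly one) |
|---|---|---|---|
| 10 mm | 0.539 | 0.374 | 0.33 |
| 12 mm | 0.695 | 0.551 | 0.29 |
| 14 mm | 0.822 | 0.718 | 0.21 |

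So in a fifth to a third of such trials, the p-values alone would point to a dose difference that does not exist.

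**The case against.** The other side has real strength.

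- **Much dose-specific output is planned.** A reader might infer that dose results appear only as comparisons with triamcinolone. The documents do not support that: means, an interval graph, curves and subsequent-flare summaries are given by dose. The point difference follows exactly by subtraction, because (200 mg − triamcinolone) − (100 mg − triamcinolone) = 200 mg − 100 mg. What is missing is its interval. The per-arm intervals give only an approximation, since they may include center variation that the contrast largely removes.
- **No rule selects a dose by p-value.** A reader might infer that the dose will be the one with the smaller p-value. No section says so, and Protocol 7.2.4.2 describes the comparison as descriptive and covering safety as well as efficacy. The 29% shows what the p-values could suggest, not what the sponsor has said it will do. Nor does the plan propose combining the two comparisons as if independent, so the inflated standard error that would result (4.86 × √2 = 6.87 mm) is not a flaw of the plan.
- **Dose selection is not a formal objective.** It stands in the rationale, and the SAP delivers what Protocol 6.2 asks. That is right, but the rationale calls it part of the main aim.
- **BMI.** Protocol 7.2.4.2 says "As the anakinra clearance increases with increasing body weight, once-daily s.c. doses of both 100 and 200 mg will be evaluated in this study", and a reader might infer that the doses must be contrasted within BMI strata. The argument there is that the gout population is heavier on average than the rheumatoid arthritis population (98 against 77 kg), not that heavier patients within the trial need a different dose. SAP 14.2.1 already plans model VAS graphs for the dose groups, also by BMI subgroup. Assuming an even BMI split, each stratum contrast would have a half-width of about 13.5 mm and the interaction about 19 mm. This part does not stand.
- **The contrast is imprecise.** It is, but no more so than the two dose comparisons that are planned with p-values.

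**Conclusion.** The point holds as a reporting gap. Dose selection is in the stated main aim and a descriptive dose comparison is announced, yet the SAP plans no 200 mg minus 100 mg estimate with an interval for any endpoint. The sample size and the formal objectives are unaffected.

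The contrast would carry a 95% half-width of about 9.6 mm. Without it, the planned p-values would split in about 29% of trials with two identical doses each 12 mm better than triamcinolone (33% at 10 mm, 21% at 14 mm). These figures assume SD 25 mm, 53 analysed patients per arm, no missing data and a normal approximation. The mixed model's actual standard errors will differ somewhat.

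**What to change.** In SAP 14.3.1.1, add the contrast anakinra 200 mg minus anakinra 100 mg for the primary endpoint, from the same mixed model: estimate and 95% CI, no p-value, labelled as descriptive in line with Protocol 7.2.4.2. Add one sentence that a difference in significance against triamcinolone will not be read as a difference between doses. Make the change before the first database lock and unblinding.

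The cost is one more contrast statement in a model already specified, with no new data or patients. The downside is a wide interval, about ±9.6 mm, which will not settle modest dose differences and should be described that way in the report.
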